### Efficacy and Safety Variables

The efficacy and safety variables in this study will be the change from the baseline assessment to the end of follow-up assessment or end of treatment assessment for the variables listed below. The variables will be determined from: the measurement of body weight, the recording of TPN prescriptions, blood and urine analyses, radiology reports, GI exams, and possible liver biopsies.

- Parenteral Nutrient Requirements (determined from the TPN/PN prescription)
  - TPN/PN infusions (days/week)
  - TPN/PN fluid volume (cc/week)
  - TPN calories (kcal/week)
  - TPN protein (g/week)
  - TPN lipid (g/week)
  - Intravenous vitamins (type and # of infusions/week)
  - Intravenous trace elements (type and # of infusions/week)
  
- Assessment of Nutritional Status
  - Body Composition
  - Body Weight
  
  - Nutrient and Metabolic Profile (Blood analyses)
  - Vitamins- A, B12, C, D, E, folate
  - Minerals and trace elements - calcium, phosphorus, iron, selenium, zinc
  - Serum Proteins - total protein, albumin, globulin
  - Lipid profile - essential fatty acids levels
  - Citrulline, D-lactic acid
  - Serum Electrolytes – (sodium, potassium, chloride, bicarbonate, magnesium)
  
- Assessment of Hydration Status/ Renal Function (Blood analyses)
  - Blood urea nitrogen
  - Serum creatinine

- Assessment of Liver Function (Blood analyses)  
Total bilirubin, direct and indirect bilirubin, alkaline phosphatase, SGOT, SGPT, LDH.
- Assessment of Upper and Lower GI tract/Liver  
Upper and Lower endoscopy, mucosal biopsies and bacterial cultures  
Ultrasound of abdomen/Small bowel follow through, Barium enema  
Liver biopsy (based on clinical indication)

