### **Side Effects (that may lead to Disruption or Discontinuation of Omegaven™):**

The infusion of Omegaven™ can lead to prolonged bleeding time and an inhibited platelet aggregation. The administration of Omegaven™ should be stopped or reduced if there is a marked increase in blood glucose levels during infusion. Undesirable effects that are seen during infusion of Omegaven™ that may also occur with conventional fat emulsions (i.e., Intralipid) include:

Slight rise in body temperature, Heat sensation and/or cold sensation, Chills, Dyspnea, Flushing or cyanosis, Lack of Appetite, nausea, vomiting, Headache, pain in chest, bone pain, Priapism, Increase/decrease in blood pressure, Anaphylactic reactions/erythema

Other expected adverse events that are common to all patients with short bowel syndrome, regardless of the type of fat emulsion they receive, include blood stream infections and re-admittance to hospital. Causes for re-hospitalization include dehydration, bloodstream infections, electrolyte abnormalities, bowel obstruction, and central venous catheter malfunction.

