## Statistical Analysis

Data from the two sets of patient population will be pooled and compared (i.e., current protocol patients prescribed Omegaven™ PN compared to historical controls where parenteral lipid calories were provided exclusively through soybean-based formulations). Potential for effect in different patient populations will be minimized by matching patients enrolled in the Omegaven™ protocol to historical controls. Frequency matching will be utilized given the difficulty of paired matching in this patient population. Specific matching criteria will include gender, age, etiology of short bowel syndrome, and severity of liver disease (parenteral nutrition- associated liver disease).

Continuous data will be expressed as mean +/- SEM. A two-way repeated measure ANOVA will be used to compare differences in the two groups with respect to changes between the Evaluation assessment and the subsequent analyses performed at Treatment and Treatment/Follow-up Assessments. Incidence of adverse events in each treatment arm will be compared using Fisher's exact test. Univariate and multivariate analysis will be used to identify baseline factors that may influence outcome. A P-value <0.05 will be considered statistically significant.

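### Sixteen vitamins, minerals and electrolytes are judged only by signed mean change, so opposite movements can offset; add a range-based comparison alongside it

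*Combined protocol and SAP*

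**What the plan says.** Under Efficacy and Safety Variables, one definition covers every listed item: "The efficacy and safety variables in this study will be the change from the baseline assessment" to the end of follow-up or treatment. The list includes:

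- "Vitamins- A, B12, C, D, E, folate" (6 variables)
- "Minerals and trace elements - calcium, phosphorus, iron, selenium, zinc" (5 variables)
- "Serum Electrolytes – (sodium, potassium, chloride, bicarbonate, magnesium" (5 variables)

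That makes 16. None has a reference range or a favourable direction.

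Statistical Analysis adds "Continuous data will be expressed as mean +/- SEM" and "A two-way repeated measure ANOVA will be used to compare differences in the two groups with respect to changes between the Evaluation assessment". Its only other between-group safety analysis is "Incidence of adverse events in each treatment arm will be compared using Fisher's exact test".

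Cut-offs or normalization do appear elsewhere. The Hypothesis refers to normalization, but only of hepatic enzymes and bilirubin. The Inclusion Criteria set a direct bilirubin threshold, and the dose-reduction text sets a triglyceride threshold. Nothing comparable exists for the 16 analytes.

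**The concern.** For an analyte with a lower and an upper limit, a rise is an improvement in a patient who starts low and a deterioration in one who starts high. A signed mean adds the two together. A group in which lows and highs are both corrected can show a mean change near zero, and so can a group in which patients drift out of range on both sides.

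These variables carry a safety label in a study that changes the lipid source. What is at stake is how a non-significant mean change is read. It could be taken as reassurance about nutritional or metabolic status when the share of patients out of range differs between groups. The protocol enrols children and adults, whose normal ranges may differ, so the same raw change need not mean the same thing in each.

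**Working it through.** The plan gives no power, SD or effect size for these analytes, so there is no stated figure to reproduce. What follows is an illustration on assumed inputs.

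**Inputs.** From the documents: 100 treated patients and a significance level of 0.05 (taken as two-sided; the plan does not say). Assumed: 100 controls, since the control number is not stated; a range of −1.96 to +1.96 in arbitrary units; abnormal patients centred at −3 or +3 and others at 0; noise SD 0.7 at each assessment; 40% abnormal at baseline; 60% of treated patients normalized; controls unchanged. The test is a t-test on change, which is the group-by-time contrast when there are two time points.

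**Mean change.** With fractions L low and H high:

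- Difference in mean change: d = 0.6 × 3 × (L − H).
- Variance of change in controls: 2 × 0.7² = 0.98.
- Variance of change in treated patients: 0.98 + 0.6 × 0.4 × 9 − d² = 3.14 − d².
- Standard error: √[(3.14 − d² + 0.98)/100].
- Power ≈ Φ(d/SE − 1.96) + Φ(−d/SE − 1.96).

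| Low / high at baseline | d | SE | d/SE | Power by formula | Power by simulation (2,000 runs) |
|---|---|---|---|---|---|
| 20% / 20% | 0 | 0.203 | 0 | 0.05 | 0.04 |
| 25% / 15% | 0.18 | 0.202 | 0.89 | 0.14 | 0.13 |
| 30% / 10% | 0.36 | 0.200 | 1.80 | 0.44 | 0.45 |
| 40% / 0% | 0.72 | 0.190 | 3.79 | 0.97 | 0.97 |

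A separate simulation of the 30/10 case gave 0.40, so 0.40 to 0.45 is a fair statement of it.

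**Out-of-range share.** An abnormal patient is measured out of range with probability Φ((3 − 1.96)/0.7) = 0.931 (the far limit adds nothing material), and a normal one with probability 2Φ(−1.96/0.7) = 0.005.

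- Controls: 0.40 × 0.931 + 0.60 × 0.005 = 0.376.
- Treated: 0.16 × 0.931 + 0.84 × 0.005 = 0.153.
- Power of Fisher's exact test: 0.94. It does not depend on the low/high split. In simulations of the balanced case it runs from 0.83 with 50 controls to 0.98 with 200.

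**Two-way harm.** Suppose 10% are abnormal at baseline, evenly split, and 25% of in-range treated patients are pushed out, equally in each direction.

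- Treated: (0.10 + 0.90 × 0.25) × 0.931 + 0.675 × 0.005 = 0.306.
- Controls: 0.10 × 0.931 + 0.90 × 0.005 = 0.098.
- Power: 0.95 for the out-of-range share and 0.05 for mean change.

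**The reverse case.** Suppose all treated patients shift by 0.5 units, with 20% low and 20% high at baseline and no normalization.

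- Mean change: SE = √(2 × 0.98/100) = 0.14; 0.5/0.14 = 3.57; power Φ(3.57 − 1.96) = 0.95.
- Out-of-range share: about 0.364 versus 0.376, with power of only 0.03 to 0.04.

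Each measure is therefore blind where the other sees.

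**The case against.** The strongest objection is that the documents do not establish two-way abnormality. They give no baseline distribution for any of the 16 analytes, do not say that lows and highs balance, and do not say that parenteral nutrition is adjusted to bring each analyte into range. A relevant excess may not exist for every vitamin. A one-sided deficiency, or a shift of the whole group, would show in the mean. This stands. A reader might infer that neither benefit nor harm in these variables can ever show, or that the ANOVA should be dropped. The documents do not support the first, and the reverse case above argues against the second.

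Harm also has a second route. Adverse experiences are recorded for every patient and compared by Fisher's test, and the side-effects text says "Causes for re-hospitalization include dehydration, bloodstream infections, electrolyte abnormalities, bowel obstruction, and central venous catheter malfunction". A clinically recorded low and a clinically recorded high do not cancel there. This stands in part. No laboratory threshold says when one of these analytes becomes an event, and the plan does not say how events are ascertained in the historical controls.

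Finally, the primary objective concerns small bowel transplantation, and the hypothesis rests on hepatic enzymes and bilirubin. Nor does the plan state that a non-significant result would be read as absence of harm. Both are correct. They limit the weight of the point, but the analytes are still named as efficacy and safety variables and have no range-based analysis.

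**Conclusion.** The point holds in a limited form. For those of the 16 analytes that can be harmful both low and high, signed mean change alone cannot separate improvement from deterioration, and a null result leaves open a difference in the share of patients out of range. The loss is near total when lows and highs balance, substantial at 30/10, and negligible when abnormality is one-sided. All the power figures rest on assumed distributions, an assumed control number and a single end assessment; none comes from trial data. The consequence is confined to nutritional and metabolic safety reporting, and conclusions on transplantation or liver tests do not depend on it.

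**What to change.** Keep the mean-change ANOVA. For these 16 analytes, add to the Statistical Analysis section:

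1. The laboratory's age-specific reference ranges, fixed before analysis.
2. Baseline-to-end shift tables by group (below, within, above range).
3. A between-group comparison of the proportion out of range that allows for baseline category, for example stratified on it, with the proportions below and above range also shown separately.
4. A statement that these are supportive safety analyses without multiplicity control.

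The cost is a few lines of text, the reference ranges and a little more analysis. No patients, visits or assays are needed beyond those the ANOVA already requires. There are more nominal comparisons: 16 combined tests at 0.05 give 16 × 0.05 = 0.8 expected false positives if there is no true difference. Testing below and above separately would make 32 tests, or 1.6, which is a reason to show the two sides descriptively and to label the set as supportive.

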## ABSTRACT

In the United States, patients dependent upon parenteral nutrition (PN) receive parenteral fat emulsions composed of soybean oils. Lipids are necessary in PN-dependent patients due to their high caloric value and essential fatty acid content. They have been implicated in predisposing patients to PN-associated liver disease, and children requiring prolonged courses of PN are at risk for developing PN-associated liver disease. Animal studies have shown that IV fat emulsions such as fish oil that are high in eicosapentaenic and docosahexaenoic acid reduce impairment of bile flow which is seen in cholestasis caused by conventional fat emulsions. We hypothesize that a fat emulsion comprised of omega-3 fatty acids (i.e., fish oil) such as Omegaven™ will be well tolerated and will reduce the inflammatory effect in the liver of prolonged PN exposure, with the potential of reversing any hepatic dysfunction due to PN/IFE use. By administering Omegaven™ in place of conventional phytosterol/soybean fat emulsions we may reverse or prevent the progression of PN associated cholestasis and thus allow the patient to be maintained on PN until they are able to ingest adequate nutrition enterally.

All patients in the Intestinal Rehabilitation Program at UNMC with an abnormal serum bilirubin (>2mg/dL), receiving PN and not meeting an exclusion criteria will be approached for enrollment. Upon enrollment, the PN lipid source will be switched to Omegaven, and patients will continue to be followed in standard fashion for ongoing intestinal rehabilitation. Patients will continue to have regular follow-up including laboratory evaluation at least once weekly, with periodic radiologic and endoscopic evaluation as per our standard of care. As hypertriglyceridemia is a possible side effect of Omegaven, weekly triglyceride levels will be added to regular labs. Patients will be continued on Omegaven until weaned from intravenous lipids per standard of care. Clinical data will be collected prospectively and will be compared with historical controls.

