We propose to conduct a prospective evaluation of the use of Omegaven™ for the provision of parenteral lipid calories in concert with an active ongoing program of intestinal rehabilitation. Our main outcome of interest will be need for small bowel transplantation, with secondary outcomes including improvement in clinical measures associated with PNALD and need for liver transplantation. This study will be conducted in both pediatric and adult intestinal rehabilitation patients.

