## STUDY PROTOCOL

### Hypothesis

Established parenteral nutrition (PN) associated liver disease can be reversed or its progression halted by using a parenteral fat emulsion prepared from fish oil as measured by normalization of serum levels of hepatic enzymes and bilirubin.

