## **Study Design**

This study will be a prospective, non-randomized, open-label study of Omegaven™ with a total enrollment of 100 patients, for provision of parenteral lipid calories. The study cohort, receiving the PN at 1g/kg/day, will be compared to historical controls at UNMC where parenteral lipid calories were provided exclusively through soybean-based formulations, as well as, assessing the study cohorts need for small bowel and liver transplantation.

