#### **2. Evaluation**

During this period, the Investigator will evaluate to confirm eligibility. All these procedures are performed at initial evaluation on all patients in the Intestinal Rehabilitation Program, regardless of entry into a study. In addition to a review of body systems, the baseline evaluations will include the recording of body weight and routine urine and blood laboratory analyses. These blood and urine analyses will determine vitamin, trace element, essential fatty acid levels, serum electrolytes, hydration status, kidney function and liver function. Patients will also have radiology and GI exams. It is possible the evaluation may include a liver biopsy. The patient's pre-study TPN prescription will also be recorded.

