#### **4. Treatment/Follow-up Period**

During the follow-up period, patients will continue to be followed by the Intestinal Rehabilitation Program per our standard care for any patient on PN: All patients in IRP are followed with regular blood work, including CBC/diff and CMP at least weekly initially, and in most cases 2-3 times per week. Based on clinical progress, the frequency of laboratory evaluation may be reduced, but is rarely less than once weekly until patients are stable and off PN. These procedures and tests would continue to be performed.

In addition to standard nutritional monitoring, essential fatty acids and serum triglycerides levels will be sent monthly. If a patient should experience lipid intolerance, then serum lipid profiles, including triglycerides, will be sent weekly for the first 4 weeks of therapy, and if stable will be reduced to every two weeks. This monitoring is additional to what would be standard in this population. Any adverse experiences will be recorded for every patient throughout the entire enrollment of the study.

Patients will remain on Omegaven™ until weaned from PN and may continue monotherapy with Omegaven™ as an additional source of calories after the dextrose/protein portion of PN is discontinued.

Upon returning home, patients will be returned to the care of the physician who referred them for participation in the study. Arrangements will be made with the patient's primary care physician to continue usual follow-up. Patients will initially be seen by their primary care physician within one week of returning home.

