#### **Measurements and Evaluations**

The following assessments will be performed at Evaluation, during the Treatment and Treatment/Follow-up Periods

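### Efficacy change has no common end time in the two groups, so the secondary liver comparison may partly measure how long patients were observed

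*Combined protocol and SAP*

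**What the plan says.** Efficacy and Safety Variables states that the variables "will be the change from the baseline assessment to the end of follow-up assessment or end of treatment assessment for the variables listed below". The list covers PN requirements, weight, nutritional blood tests and liver function. No week or month is attached.

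For the Omegaven cohort, two sections describe when these ends occur:
- **End of treatment** (Patient Discontinuation, Discontinuation of Therapy): the patient is off PN, develops a contraindication, or the patient or family asks to leave.
- **End of follow-up** (the earlier section Discontinuation of Therapy): the programme follows patients until they have no remaining rehabilitation needs and eat a full oral diet.

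Other sections word the end of treatment differently. The Abstract says "Patients will be continued on Omegaven until weaned from intravenous lipids per standard of care". Treatment/Follow-up Period says "Patients will remain on Omegaven™ until weaned from PN", then allows Omegaven to continue alone after the dextrose and protein part has stopped. Duration of Therapy repeats this.

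Under Study Design, the cohort "will be compared to historical controls at UNMC where parenteral lipid calories were provided exclusively through soybean-based formulations". No baseline date, end of treatment or end of follow-up is given for those controls.

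Statistical Analysis plans a two-way repeated-measures ANOVA of change from Evaluation to the Treatment and Treatment/Follow-up assessments. Measurements and Evaluations says only: "The following assessments will be performed at Evaluation, during the Treatment and Treatment/Follow-up Periods".

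**The concern.** A change score has a clear meaning only if both groups are measured over the same span. Here the span is set by each patient's course in one group and is not set at all in the other. Bilirubin and enzymes may drift over months in either direction. A group observed for longer then shows more drift even if the drug does nothing.

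The analyst could also choose either end point after seeing the data, because both fit the text.

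The liver comparison is at stake. It is a secondary objective, but the Hypothesis is to be judged "as measured by normalization of serum levels of hepatic enzymes and bilirubin", so the trial's stated scientific claim rests on it.

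**Working it through.** **Reading.** The plan states no effect size, slope, SD, exit rate, follow-up length or number of controls, so there is no figure to reproduce. The first check is whether any section supplies the missing time.

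| Where a time might be found | What it gives |
|---|---|
| Efficacy and Safety Variables | two alternative ends, no rule |
| Patient Discontinuation; Discontinuation of Therapy | event-driven ends, Omegaven cohort only |
| Treatment/Follow-up Assessments | list of tests, no dates |
| Study Design (controls) | lipid source only |
| Statistical Analysis | named periods, not times |

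None gives a time common to both groups.

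**Closed form.** Assume no drug effect, log bilirubin changing at the same mean slope b per month in both groups, and exit unrelated to bilirubin. Then

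bias in mean log change = b × (mean months observed, Omegaven − controls).

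The slopes are assumed, as is a 6-month difference:
- b = 0.02: exp(0.02 × 6) = exp(0.12) = 1.13
- b = 0.05: exp(0.05 × 6) = exp(0.30) = 1.35
- no difference in months: exp(0) = 1.00

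A falling trend gives the reciprocals.

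**Illustrative simulation, no drug effect.** Two inputs come from the documents: 100 Omegaven patients, and 2 mg/dL as the lower limit of baseline bilirubin (the plan's limit is for direct bilirubin). The rest are assumptions:
- 100 controls, 24 months' follow-up, monthly steps
- baseline uniform from 2 to 10 mg/dL
- log slope per month normal, mean −0.02 or +0.03, SD 0.05, 0.08 or 0.12
- true value B held within 0.3 to 40 mg/dL; lognormal measurement error, SD 0.15
- monthly probability of transplant 0.025 × B/5 and of weaning 0.025 × √(5/B), each multiplied by 1, 1.25 or 2 in controls and capped at 0.5

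The test is a two-sample t-test of change from baseline to the last value before exit or cut-off, at 0.05.

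| Exit rate in controls | False positives, mg/dL | False positives, log scale |
|---|---|---|
| equal | about 4–6% | about 4–6% |
| 1.25 times | about 5–10% | about 4–8% |
| 2 times | about 5–55% | about 5–24% |

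Ranges run over the six slope settings. Rates near 40–55% occur only in raw mg/dL, with mean slope +0.03 and doubled exit.

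**Check of the closed form.** With exit unrelated to bilirubin (0.025 per month for each route, doubled in controls) and slope −0.02, mean time observed differs by 4.96 months. The formula gives −0.02 × 4.96 = −0.099; the simulation gives −0.103 log units.

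**Direction.** At mean slope −0.02, SD 0.12 and doubled exit that depends on bilirubin, the null difference is −0.10 log units (Omegaven looks better) but +1.4 mg/dL (Omegaven looks worse). Skewness causes the reversal, so no direction can be predicted.

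**The case against.** **The ANOVA already includes time.** It includes period. A Treatment/Follow-up value could come from month 3 in one patient and month 30 in another, so the named periods do not supply a time.

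**The cohort's ends are defined.** This stands in part: event-based ends are stated for both treatment and follow-up. They depend on recovery, tolerance or withdrawal, and controls have no counterpart.

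**Liver measures are secondary.** True. The main outcome is stated as "Our main outcome of interest will be need for small bowel transplantation". A reader might infer that the change-score wording undermines that outcome too. It does not, because that sentence does not define the transplant outcome. The sections that name the outcome give it no time horizon, but that is a separate gap.

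**The high error rates rest on one extreme assumption.** This stands. Nothing in the documents supports a doubled exit rate or 100 controls. At 1.25 times the exit rate the inflation is small on either scale, and the log transform alone removes much of what appears in mg/dL.

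**Matching could cover follow-up length.** A reader might infer that leaving it out is a defect. It is not: follow-up arises after baseline and depends on outcome, so it is not a suitable matching factor.

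**The end-of-treatment statements contradict each other.** A reader might infer this too. The Abstract and the list of PN requirements treat lipid as part of PN, and on that reading the statements can agree. Treatment, which allows Omegaven alone or together with PN, points the other way. Clarification is enough.

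**Conclusion.** The concern holds in conditional form and should be fixed. The plan sets no common time for efficacy change, no rule for choosing between two ends, and no index date or end point for controls. Bias in the liver comparison needs both a time trend and a difference in exit or follow-up. No section prevents either.

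Its size and direction in this trial are unknown. The ratios of 1.13 to 1.35 rest on assumed slopes, an assumed 6-month difference and exit unrelated to bilirubin. The simulated error rates are illustrations, not bounds. A reader might infer that the trial has about an even chance of a false liver finding, or that the bias favours Omegaven. The documents support neither.

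**What to change.** **Efficacy and Safety Variables.** Define change in laboratory, PN-requirement and weight variables at the same fixed times in both groups, for example 3, 6 and 12 months, limited to times that both groups' follow-up covers.

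**Index date.** Base eligibility only on criteria that can be applied to both groups: programme enrolment, direct bilirubin of 2 mg/dL or more, and expected PN need of at least 30 days. Leave out signed consent, which historical controls did not give for this study. The Evaluation section offers a starting point for baseline data: "All these procedures are performed at initial evaluation on all patients in the Intestinal Rehabilitation Program, regardless of entry into a study". Take the start of Omegaven as time zero for treated patients. For controls, use an assessment that meets the same criteria, chosen by a rule fixed in advance and at a comparable time since first eligibility. Untreated waiting time is then not counted as Omegaven time.

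**Statistical Analysis.** Replace the period-based ANOVA with a mixed model on actual sampling dates, containing baseline value, group, time, group-by-time and the matching factors (log scale for bilirubin if skewed). Exclude laboratory values after a liver-containing transplant. Add one simple sensitivity analysis for informative exit through death, transplant, weaning or withdrawal, such as shifting the unobserved values and reporting the shift that changes the conclusion.

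**Clarification.** Reconcile the end-of-treatment wording in the Abstract, Treatment, Treatment/Follow-up Period, Duration of Therapy and Patient Discontinuation.

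**Cost.** Protocol and SAP wording plus moderate programming. Blood work is described as at least weekly at first, but the panels are at the investigator's discretion. Dated laboratory values and follow-up dates for controls are not documented and must be confirmed first. The mixed model needs more explanation than ANOVA and assumes that exit depends on observed values, hence the sensitivity analysis.

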#### **Treatment/Follow-up Assessments**

- Parenteral Nutrient Requirements (same as the Evaluation Period)
- Assessment of Nutritional Status (same as the Evaluation Period)
- Assessment of Hydration Status/ Renal Function (same as the Evaluation Period)
- Assessment of Liver Function (same as the Evaluation Period)
- Parenteral Nutrient Requirements (same as the Evaluation Period)
- Signs and Symptoms

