### **Duration of Therapy**

Patients will remain on Omegaven™ until weaned from PN and may continue monotherapy with Omegaven™ as an additional source of calories after the dextrose/protein portion of PN is discontinued.

In the event that a patient is listed for a liver or liver/intestinal transplant and an organ becomes available, the participation in this protocol will not preclude them from receiving the transplant.

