### **Discontinuation of Therapy**

Patients will continue to be followed by the UNMC Intestinal Rehabilitation Program upon discontinuation of therapy with Omegaven™ until they are completely free of any rehabilitation needs and are tolerating a full diet by mouth.

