### **Discontinuation of Therapy –**

- In the event that a patient is unable to achieve adequate calories parenterally and is unable to tolerate enteral feeds, it may be necessary to evaluate whether or not the patient should continue the study with Omegaven™ as monotherapy or resume therapy with conventional fat emulsions so that additional parenteral fat calories can be given.
- Adverse Event (AE) – Any patient with anaphylactic or allergic reactions to Omegaven™ will not continue treatment and will be withdrawn from the protocol.
- Inter-current Illness – If a patient develops an illness during the course of the study that is not associated with the condition under study and that requires treatment inconsistent with the protocol requirements (such as an interruption of regular participation in the study), the patient may be discontinued from further participation in the study. A patient may also be discontinued from the study if he develops an inter-current illness or complication that in any way justifies his withdrawal from the study. However, if an inter-current illness develops which can be managed without significant interference with the requirements of the protocol, the patient need not be discontinued.
- The patient will complete treatment with Omegaven™ in this study when he/she is completely off PN, develops a contraindication for further use, or the patient/family requests to be removed from the study.

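### Liver outcomes run to an unspecified end assessment with no cut-off at transplant, so tests from a grafted liver can enter the secondary liver comparison

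*Combined protocol and SAP*

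**What the plan says.** - **End point.** Under Efficacy and Safety Variables, the variables "will be the change from the baseline assessment to the end of follow-up assessment or end of treatment assessment". The list includes total, direct and indirect bilirubin, alkaline phosphatase, SGOT, SGPT and LDH.
- **Claim to be tested.** The Hypothesis is that established liver disease is reversed or halted, "as measured by normalization of serum levels of hepatic enzymes and bilirubin". It does not restrict this to the native liver.
- **Transplant is expected.** Small bowel transplantation is the primary objective, and Background and Rationale makes need for liver transplantation a secondary outcome. Duration of Therapy adds: "In the event that a patient is listed for a liver or liver/intestinal transplant and an organ becomes available", taking part in the study does not stand in the way.
- **End of treatment.** Under Patient Discontinuation, a patient completes Omegaven "in this study when he/she is completely off PN, develops a contraindication for further use", or on request of the patient or family. Transplant is not listed.
- **End of follow-up.** The earlier Discontinuation of Therapy section, under the dosing material, says "Patients will continue to be followed by the UNMC Intestinal Rehabilitation Program upon discontinuation of therapy", until no rehabilitation need remains and the patient eats a full oral diet. Transplant is not an end here either.
- **Analysis.** Statistical Analysis states: "A two-way repeated measure ANOVA will be used to compare differences in the two groups with respect to changes". The changes run from baseline to later values in the treatment and follow-up periods. The section does not mention transplant, death, missing data or values after an event.

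**The concern.** A liver-containing graft replaces the organ whose disease is under study. Normal bilirubin afterwards says nothing about whether fish oil reversed the disease; in that patient the native liver had to be replaced. If the last follow-up value is used as it stands, a failure on Omegaven or on soybean lipid looks like a large improvement.

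The open choice of end assessment adds to this. For one patient, end of treatment may show the failing native liver and end of follow-up the graft. Choosing end of treatment does not settle it: treatment ends when the patient is off PN, which can come after a transplant, and historical controls have no end of Omegaven treatment. Being off PN is a possible counterpart for them, but the plan does not say that it will be used.

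At stake is the secondary liver comparison, which tests the stated hypothesis. In an open-label comparison with historical controls, an end point left open until the data are seen also leaves room for selection.

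**Working it through.** **Figures in the plan.** There is none to reproduce. The documents give 100 Omegaven patients and a 0.05 significance level. They give no number of controls, effect size, SD, transplant rate or power.

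**Reading the sections together.** Transplant is foreseen, ends neither treatment nor follow-up, and is not a cut-off in the analysis section. No other section supplies one. So graft values are not kept out of the comparison.

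**Illustration: inputs, all assumed except the 100 Omegaven patients and the 0.05 level**
- 100 controls; two-sided t test.
- Direct bilirubin at baseline 6.0 mg/dL. Native-liver change -2.0 on Omegaven and 0 in controls, SD 4, so the true difference is 2.00.
- A graft ends at 0.6, a change of 0.6 - 6.0 = -5.4, SD 1.
- t_O and t_C are the shares with a liver-containing transplant in the Omegaven and control groups.

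**Last value only**
- Group mean change = (1 - t) × native change + t × (-5.4).
- Group variance = (1 - t) × 16 + t × 1 + t(1 - t) × (native change + 5.4)².
- Difference (control minus Omegaven) = 2.00 + 3.4 t_O - 5.4 t_C.

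Worked case, 5% versus 15%: 2.00 + 3.4 × 0.05 - 5.4 × 0.15 = 2.00 + 0.17 - 0.81 = 1.36. Variances are 15.80 and 17.47, so SE = √(33.27/100) = 0.577. The noncentrality is 1.36/0.577 = 2.36 and power is 65%. With no transplants, SE = √(32/100) = 0.566, the noncentrality is 3.54 and power is 94%.

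| Omegaven vs control transplants | Difference (mg/dL) | Power |
|---|---|---|
| 0% vs 0% | 2.00 | 94% |
| 5% vs 5% | 1.90 | 91% |
| 5% vs 10% | 1.63 | 81% |
| 5% vs 15% | 1.36 | 65% |
| 5% vs 25% | 0.82 | 29% |
| 10% vs 5% | 2.07 | 95% |
| 15% vs 5% | 2.24 | 98% |

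**Direction with a real benefit.** The difference exceeds 2.00 only if 3.4 t_O > 5.4 t_C, that is t_O/t_C > 5.4/3.4 = 1.59. At 6% versus 5% it is 2.00 + 0.204 - 0.27 = 1.93, still diluted.

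**No true effect** (native change 0 in both groups), 15% versus 5%: false difference = 5.4 × (0.15 - 0.05) = 0.54 mg/dL. Variances are 17.47 and 16.64, SE = 0.584, noncentrality 0.92, rejection rate 15% against a nominal 5%.

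**More than one value per patient.** If k pre-transplant changes are averaged equally with the last one, the difference at 5% versus 15% is (2.00k + 1.36)/(k + 1): 1.68 for k = 1 and 1.92 for k = 7. The false difference at 15% versus 5% is 0.54/(k + 1): 0.27 and 0.07.

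**Native-liver values only.** In a simulation with two time points, correlation 0.6 and 6,000 runs, values after transplant were set to missing and a likelihood-based model was fitted. The estimated difference was 1.99 to 2.02, power 91% to 94% and the false-positive rate 4.5% to 5.4%. This is a best case, because transplant was assumed unrelated to the native-liver value.

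**The case against.** The strongest reply has five parts.

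1. *Patients can be withdrawn.* Investigators may discontinue anyone at any time, and a complication can justify withdrawal. True, but this is discretion and not a rule, and it cannot be applied to historical controls.
2. *Program follow-up is not necessarily study data.* The text on follow-up after Omegaven stops describes care by the rehabilitation program. That graft values reach the dataset is possible, not certain. This stands as a limit on the claim; it does not supply the missing cut-off.
3. *Repeated values dilute the effect.* Chemistries are planned about weekly, so many native-liver values may precede a graft value. This stands. The last-value figures are upper bounds, and the one-value average (1.68) is not a floor. A group-by-time test would equal neither the last-value nor the averaged comparison.
4. *No responder count is planned.* A reader might infer that the plan will score transplanted patients as reversals. The documents do not support that: normalisation appears in the Hypothesis, while Statistical Analysis compares changes by ANOVA. The risk lies in that comparison and in any later statement on normalisation.
5. *Liver transplantation is itself an outcome.* Reporting it would show an imbalance, but would not remove graft values from the ANOVA.

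A reader might also infer that any excess of transplants on Omegaven overstates a real benefit. Under these inputs it does so only above about 1.6 times the control rate, and then modestly.

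**Conclusion.** The gap in the text is clear: the end assessment is not chosen, and nothing keeps liver values from a graft out of the secondary comparison. It should be fixed. The primary outcome is not affected.

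Size and direction cannot be derived from the documents. With a real benefit, graft values dilute the difference unless the Omegaven rate of liver-containing transplant is well above the control rate. With no true effect, unequal rates create a false difference. Low, equal rates do little harm (1.90 against 2.00 at 5% in each group). The last-value losses in power and the 15% false-positive rate rest on assumed transplant rates, SDs, graft values and control numbers. They show what could happen; they do not predict this study. A reader might take the fall to 65% power as the expected loss, but the documents do not support that, since the number of pre-transplant values entering the ANOVA is not stated.

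**What to change.** **Efficacy and Safety Variables, and Statistical Analysis.** Name one analysis time, defined the same way in both groups. Fix it after checking what the control charts support and before the groups are compared. Add: *Liver values taken on or after a liver-containing transplant are not used. For any statement on reversal, death or liver-containing transplant by the analysis time counts as not reversed.*

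**Statistical Analysis.** Replace the classical repeated measures ANOVA for liver values with a baseline-adjusted, likelihood-based mixed model on the repeated native-liver values. Series ended by death, transplant or weaning then still contribute. Because this model assumes data missing at random, add one sensitivity analysis that ranks death worst, then liver-containing transplant, then observed values.

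**Cost.** Wording, a check of control charts for dated transplants and liver values, and more analysis work. The reported normalisation rate may be lower. Some late liver values will be missing, because liver tests are partly at the investigator's discretion and are not assured after weaning. Report how many are missing rather than adding a test.
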